For the change from baseline at Month 12 in the 6-MWT, assuming a treatment difference of 33 meters between patisiran and placebo in the treatment-naïve group and 20 meters in patients with baseline tafamidis, the weighted average treatment difference between patisiran and placebo in the overall population is approximately 29 meters (standard deviation = 75 meters) assuming 70% are in the treatment-naïve group and 30% are in the baseline tafamidis group. A sample size of 300 patients provides >90% power for a 2-sided test to detect a treatment difference at a 2-sided alpha = 0.05. Additional patients may be enrolled based on a recommendation to increase the sample size in the interim assessment.

The primary endpoint, change from baseline at Month 12 in the 6-MWT, will be analyzed using a mixed-effects model repeated measures (MMRM) approach. The outcome variable is change from baseline in the 6-MWT. The model will include the baseline value as a covariate, treatment, visit, baseline tafamidis (yes vs no), genotype (hATTR vs wtATTR), age (<75 vs ≥75 years), the treatment-by-visit interaction, the treatment-by-baseline tafamidis interaction, the visit-by-baseline tafamidis interaction, and the treatment-by-visit-by-baseline tafamidis interaction as fixed factors. The primary comparison is the contrast (difference in least squares [LS] means) between the patisiran and placebo groups at Month 12.

To control the overall Type I error rate, secondary endpoints will be tested in a prespecified hierarchical order.

For patients who are tafamidis treatment-naïve at baseline and start tafamidis during the double-blind period, the primary analysis of the primary endpoint will censor data collected after the initiation of tafamidis treatment post-randomization.

Safety data will be summarized descriptively.

Figure 1: Study Design

[figure not shown]

Table 1: Year 1 Schedule of Assessments: Double-blind Period (Screening to Month 12 Efficacy Assessments)

Table 1: Year 1 Schedule of Assessments: Double-blind Period (Screening to Month 12 Efficacy Assessments)

Study Day ±Visit Window	For Details see Section	Screen- ing		Baseline		Double-blind Treatment Period																																										
		V1	V2	Pre- dose	Post- dose																																											
		Day -45 to Day -1		Day 1																																												

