evidence of HF (with or without hospitalization) manifested by signs and symptoms of volume overload or elevated intracardiac pressures (eg, elevated jugular venous pressure, shortness of breath or signs of pulmonary congestion on x-ray or auscultation, peripheral edema) that currently requires treatment with a diuretic.

4. Patient meets one of the following criteria:
 - a. Tafamidis naïve; in addition to patients who have never taken tafamidis, those who have been on tafamidis for ≤ 30 days total and have not received any tafamidis in the 6 months prior to baseline will be considered tafamidis naïve and may qualify for the study.
 - b. Currently on tafamidis (for ≥ 6 months) and has demonstrated disease progression, as determined by the Investigator. (At the time of study entry, tafamidis treatment must be on-label use of commercial tafamidis for the treatment of ATTR amyloidosis with cardiomyopathy at the approved dose in the country of use.)
5. Patient is clinically stable, with no CV-related hospitalizations within 6 weeks prior to randomization, as assessed by the Investigator.
6. Able to complete ≥ 150 m on the 6-MWT at screening.
7. Screening NT-proBNP >300 ng/L and <8500 ng/L; in patients with permanent or persistent atrial fibrillation, screening NT-proBNP >600 ng/L and <8500 ng/L.

Informed Consent

8. Patient is able to understand and is willing and able to comply with the study requirements and to provide written informed consent; and patient agrees to sign the medical records release form for collection of vital status.

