6.2.5.1. Cardiac Biomarkers

The cardiac biomarkers NT-proBNP and troponin I will be used to assess cardiac stress and heart failure severity. These biomarkers have been shown to be prognostic of outcomes in HF, including in ATTR amyloidosis.[[Damy 2016](#); [Kristen 2017](#); [Merlini 2016](#)] Blood samples will be drawn to measure cardiac biomarker levels at the timepoints specified in the Schedule of Assessments ([Table 1](#), [Table 2](#), [Table 3](#), and [Table 4](#)) and will be measured at a central laboratory. At screening Visit 1, only NT-proBNP will be assessed for eligibility purposes.

Details on cardiac biomarker sample collection, processing, and storage will be provided in a Study Laboratory Manual.

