7.2.5.1. Primary Endpoint

The primary endpoint, change from baseline at Month 12 in the 6-MWT, will be analyzed using a mixed-effects model repeated measures (MMRM) approach. The outcome variable is change from baseline in the 6-MWT. The model will include the baseline value as a covariate, treatment, visit, baseline tafamidis (yes vs no), genotype (hATTR vs wtATTR), age (<75 vs ≥ 75 years), the treatment-by-visit interaction, the treatment-by-baseline tafamidis interaction, the visit-by-baseline tafamidis interaction, and the treatment-by-visit-by-baseline tafamidis

interaction as fixed factors. The primary comparison is the contrast (difference in least squares [LS] means) between the patisiran and placebo groups at Month 12.

Sensitivity analyses will be detailed in the SAP.

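### The primary 6-MWT model could also adjust for baseline NT-proBNP, which every eligible patient already has: a near-costless efficiency gain of uncertain size, not an error

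*Protocol*

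**What the plan says.** The synopsis (Statistical Methods) and Section 7.2.5.1 give the same primary model. In Section 7.2.5.1, "The outcome variable is change from baseline in the 6-MWT". On the terms, the synopsis states "The model will include the baseline value as a covariate, treatment, visit, baseline tafamidis (yes vs no), genotype (hATTR vs wtATTR" and continues with age (below 75 versus 75 and over) and the two-way and three-way interactions of treatment, visit and baseline tafamidis. NT-proBNP does not appear. Section 7.2.5.2 says only that KCCQ-OS will have a model similar to the primary one.

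Elsewhere the protocol gives NT-proBNP a prominent role. Inclusion criterion 7 in Section 4.1 requires "Screening NT-proBNP >300 ng/L and <8500 ng/L", with a higher lower limit of 600 ng/L in permanent or persistent atrial fibrillation. Section 6.2.5.1 has NT-proBNP and troponin I measured centrally to assess cardiac stress and heart-failure severity, and adds: "These biomarkers have been shown to be prognostic of outcomes in HF, including in ATTR amyloidosis".

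On power, the synopsis states: "A sample size of 300 patients provides >90% power for a 2-sided test to detect a treatment difference at a 2-sided alpha = 0.05".

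**The concern.** A baseline variable that predicts the outcome beyond the terms already in the model reduces residual variance and narrows the confidence interval for the treatment contrast, without any further patients. NT-proBNP is a natural candidate. The protocol itself calls it prognostic, it is measured before treatment in everyone eligible, and conditioning on it excludes no one. The eligibility limits also leave room for wide variation between patients (8500/300 is about 28-fold, or 8500/600, about 14-fold, in atrial fibrillation), although these are limits and not a distribution.

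Heart-failure severity is used in other parts of the design. NYHA class forms part of the third stratification factor and is a covariate in the modified Andersen-Gill model of Section 7.2.5.2. The primary MMRM carries only the age part of that stratum. At stake is some precision on the 6-MWT test, which gates every secondary endpoint, and on KCCQ-OS, the first secondary endpoint.

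**Working it through.** **Inputs from the protocol.** Total N = 300, randomized 1:1, so 150 per arm; two-sided alpha 0.05; effect and SD as in "the weighted average treatment difference between patisiran and placebo in the overall population is approximately 29 meters (standard deviation = 75 meters".

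**Input assumed.** r is the partial correlation of baseline (log) NT-proBNP with Month 12 change in 6-MWT, given the terms already in the model. The protocol gives no value, so the range 0 to 0.3 is shown. The 75 m is read as the residual SD of the planned model. The protocol does not say whether it is.

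**Step 1: the plan's own figures.** The synopsis works from "assuming a treatment difference of 33 meters between patisiran and placebo in the treatment-naïve group and 20 meters in patients with baseline tafamidis", and "assuming 70% are in the treatment-naïve group and 30% are in the baseline tafamidis group".

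- Weighted effect = 0.7 × 33 + 0.3 × 20 = 23.1 + 6.0 = 29.1 m, stated as about 29 m.
- SE = 75 × √(2/150) = 8.66 m.
- Power = Φ(29/8.66 − 1.96) = Φ(1.389) = 91.8%.
- A noncentral t calculation gives 91.6%. For 90% power, 141 per arm (282 in total) would be enough.

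The claim of more than 90% power reproduces with no NT-proBNP adjustment.

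**Step 2: effect of the added covariate.** Residual SD = 75 × √(1 − r²); SE = residual SD × √(2/150); power = Φ(29/SE − 1.96); equivalent unadjusted N = 300/(1 − r²).

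| Assumed r | Residual SD (m) | SE (m) | 95% CI half-width (m) | Power | Equivalent N |
|---|---|---|---|---|---|
| 0 | 75.0 | 8.66 | 17.0 | 91.8% | 300 |
| 0.1 | 74.6 | 8.62 | 16.9 | 92.0% | 303 |
| 0.2 | 73.5 | 8.49 | 16.6 | 92.8% | 312 |
| 0.3 | 71.6 | 8.26 | 16.2 | 94.0% | 330 |

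The gain in power is about 0.3, 1.0 and 2.2 percentage points at r = 0.1, 0.2 and 0.3. The standard error falls by 0.5%, 2.0% and 4.6%.

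**Step 3: cost if the covariate predicts nothing.** One wasted degree of freedom inflates the standard error by about √(1 + 1/292) = 1.0017, that is, about 0.2%.

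**KCCQ-OS.** The protocol gives no SD for this score, so no gain in points can be computed. The relative reduction in standard error is the same function of that endpoint's own r.

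**The case against.** The strongest reply is that nothing here is wrong. Randomization makes the contrast valid with or without NT-proBNP, the power claim holds as written, and one more prognostic covariate is a preference among many candidates. That stands, and it is why this is put as an improvement.

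Several stronger readings are tempting, and the documents do not support them.

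- *That precision is known to be lost.* Section 6.2.5.1 speaks of prognosis for heart-failure outcomes. It says nothing about 12-month change in walk distance or KCCQ-OS after adjustment for the baseline score, age, genotype and tafamidis. The gain could be nil. If 75 m is an unadjusted SD, the planned model may already exceed 91.8% power, and the added power would be smaller.
- *That the model ignores disease severity.* It adjusts for baseline 6-MWT, which Section 1.4 presents as a clinically relevant measure of functional capacity used in heart failure. That is a partial measure of severity, so NT-proBNP matters only for what it adds.
- *That the survival medians in Section 6.2.5.2 show Month 12 missingness to be driven by NT-proBNP.* Those stages combine NT-proBNP with eGFR, and this trial enrolls a selected population: for example, NYHA Class III with Stage 3 disease is excluded. No trial mortality by NT-proBNP can be read from them. The MMRM also uses the observed Month 6 and Month 9 walks, and missing-data handling is left to the SAP.
- *That the KCCQ-OS model is fixed without NT-proBNP.* It is described only as similar to the primary model, which leaves its exact terms open.

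**Conclusion.** The omission from the primary model is a fact of the protocol, in both the synopsis and Section 7.2.5.1. It is a modest missed opportunity for efficiency. It does not undermine the primary test or the sample size. Under an assumed partial correlation of 0 to 0.3, and with 75 m as the residual SD, adjustment would move power from 91.8% to at most about 94.0%, equivalent to between 0 and about 30 extra patients. The upper end depends wholly on the assumed r; up to r = 0.2 the gain is no more than about one percentage point. The case for acting rests on the imbalance between that possible gain and a worst-case cost of about 0.2% in the standard error. A more plausible missing-at-random assumption may be a secondary benefit, but it cannot be quantified from the documents.

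**What to change.** Before unblinding, amend the model statement in the synopsis and Section 7.2.5.1 to include log-transformed baseline NT-proBNP as a continuous covariate, using the screening value if the Day 1 value is missing. The log scale suits the wide eligibility range. Specify the same term explicitly in the KCCQ-OS MMRM. Keep the currently stated model as a prespecified sensitivity analysis, so that the effect of the added covariate can be seen.

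The cost is one term in the model statement and one degree of freedom. No new data, visits or patients are needed.

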LIST OF ABBREVIATIONS AND DEFINITIONS OF TERMS

Abbreviation	Definition
ADA	Antidrug antibody
AE	Adverse event
ALN-18328	siRNA targeting TTR
ALP	Alkaline phosphatase
ALT	Alanine aminotransferase
APOLLO	Patisiran pivotal Phase 3 clinical study ALN-TTR02-004
AST	Aspartate aminotransferase
ATTR	Amyloid transthyretin
BMI	Body mass index
BUN	Blood urea nitrogen
CHF	Congestive heart failure
C _{max}	Maximum plasma concentration at end of infusion
C _{max,ss}	Steady-state C _{max}
C _{min}	Minimum pre-infusion concentration
C _{min,ss}	Steady-state C _{min}
CMR	Cardiac magnetic resonance
Con Meds	Concomitant medication
COVID-19	Coronavirus disease 2019
C _{p(30min)}	30-minute post-infusion concentration
C _{p,ss(30min)}	Steady-state C _{p(30min)}
CRF	Case report form
CFR	Code of Federal Regulations
CV	Cardiovascular
DLin-MC3-DMA	1,2-Dilinoleyoxy-N,N-dimethylpropylamine
DMC	Data Monitoring Committee
DSPC	1,2-Distearoyl-sn-glycero-3-phosphocholine
ECG	Electrocardiogram
eCRF	Electronic case report form
eGFR	Estimated glomerular filtration rate
ELISA	Enzyme-linked immunoassay
EOS	End of study

Abbreviation	Definition
EU	European Union
FAS	Full analysis set
FSH	Follicle-stimulating hormone
GCP	Good Clinical Practice
H1	Histamine 1 receptor
H2	Histamine 2 receptor
hATTR	Hereditary ATTR
HF	Heart failure
ICF	Informed consent form
ICH	International Council on Harmonisation
IEC	Independent Ethics Committee
IND	Investigational New Drug
INR	International normalized ratio
IRB	Institutional Review Board
IRR	Infusion-related reaction
IRS	Interactive Response System
IV	Intravenous(ly)
KCCQ	Kansas City Cardiomyopathy Questionnaire
KCCQ-OS	Kansas City Cardiomyopathy Questionnaire– Overall Summary
LNP	Lipid nanoparticle
LS	Least squares
mBMI	Modified body mass index
MDRD	Modification of diet in renal disease
MedDRA	Medical Dictionary for Regulatory Activities
MGUS	Monoclonal gammopathy of undetermined significance
MMRM	Mixed-effects model repeated measures
mNIS+7	Modified neurological impairment score +7
mRNA	Messenger ribonucleic acid
6-MWT	6-minute walk test
NA	Not applicable
Norfolk QoL-DN	Norfolk Quality of Life - Diabetic Neuropathy
NSAID	Nonsteroidal anti-inflammatory drug

Abbreviation	Definition
NT-proBNP	N-terminal prohormone B-type natriuretic peptide
NYHA	New York Heart Association
OLT	Orthotopic liver transplantation
PCR	Polymerase chain reaction
PD	Pharmacodynamics
PEG ₂₀₀₀ -C-DMG	3-N-[(ω -methoxy poly(ethylene glycol)2000) carbamoyl]-1,2-dimyristyloxy-propylamine
PK	Pharmacokinetic
PND	Polyneuropathy disability
PT	Preferred term
RBC	Red blood cell
RBP	Retinol binding protein
RISC	RNA-induced silencing complex
RNA	Ribonucleic acid
RNAi	RNA interference
SAE	Serious adverse event
SAP	Statistical analysis plan
SOC	System Organ Class
SUSAR	Suspected unexpected serious adverse reaction
siRNA	Small interfering RNA
Tc	Technetium
TTR	Transthyretin
ULN	Upper limit of normal
US	United States
V30M	Valine to methionine mutation at position 30
V122I	Valine to isoleucine mutation at position 122
wt	Wild type
wtTTR	Wild type transthyretin

1. INTRODUCTION

1.1. Disease Overview

Transthyretin (TTR)-mediated amyloidosis (ATTR amyloidosis) is a rare, serious, life-threatening, multisystemic disease encompassing hereditary ATTR (hATTR) amyloidosis and wild-type ATTR (wtATTR) amyloidosis, which result from either hereditary (genetic mutation) or nonhereditary (ageing) causes, respectively. In ATTR amyloidosis, deposition of TTR in various organs results in progressive, chronically debilitating morbidity and mortality. The most common manifestations of ATTR amyloidosis are polyneuropathy and cardiomyopathy (ie, ATTR amyloidosis with cardiomyopathy).

TTR, also known as prealbumin, is a tetrameric protein produced by hepatocytes, the choroid plexus, and retina.[\[Liz 2010\]](#) More than 95% of TTR in the circulation is derived from the liver. The primary physiological role of TTR is to serve as a carrier of retinol (also known as vitamin A), which involves TTR binding to the retinol binding protein (RBP): vitamin A complex. However, there is evidence to suggest that vitamin A transport and tissue uptake can occur in the absence of circulating RBP.[\[Biesalski 1999; Episkopou 1993\]](#)

In hATTR amyloidosis, inherited mutations in the TTR gene lead to destabilization of the tetrameric protein and disassociation of the TTR subunits into dimers and individual mutant and wild-type (wt) monomers, which subsequently misfold. These misfolded TTR monomers can then self-assemble into oligomers and form amyloid fibrils and plaques in the extracellular space of various tissues [\[Hou 2007\]](#), including the peripheral nervous system, heart, gastrointestinal tract, kidney, central nervous system and eye, leading to cellular injury and organ dysfunction with corresponding clinical manifestations. Since almost all patients are heterozygous for the mutated TTR allele, the amyloid fibrils typically consist of both mutant and wtTTR.

There are over 120 reported TTR genetic mutations associated with hATTR amyloidosis, and almost all patients are heterozygous for the mutated TTR allele.[\[Ando 2013; Connors 2003\]](#) The phenotypic expression varies depending on the predominant site of deposition of the amyloid fibrils with some mutations associated with predominantly polyneuropathy manifestations and others associated with predominantly cardiomyopathy manifestations. However, most patients experience both over the course of their disease.

The most common TTR mutation is the valine to methionine mutation at position 30 (V30M), accounting for approximately 50% of cases worldwide, and occurring primarily in families with heritage from Portugal, Sweden, Japan, and Brazil.[\[Parman 2016\]](#) This genotype is most commonly associated with multisystemic polyneuropathy. The valine to isoleucine at position 122 (V122I) mutation is most commonly associated with cardiomyopathy and occurs primarily in African Americans. In these individuals, the mean age at diagnosis is approximately 65 to 70 years, with symptom onset typically occurring after the age of 65.[\[Jacobson 2011; Quarta 2015\]](#) While there appears to be an association between carrier status and the development of heart failure (HF) and echocardiographic features of cardiac amyloidosis, the exact penetrance of this particular allele is unknown, and estimates vary widely.

Normal, nonmutant wtTTR alone can also be amyloidogenic; this is the basis for the nonhereditary, wtATTR amyloidosis. This is a progressive disease typically seen in patients older than 70 years and is predominantly seen in men.[\[Westerman 2003\]](#) Patients with this

condition do not have a pathogenic mutation in the TTR gene and the amyloid fibrils consist only of wtTTR protein, which form amyloid deposits typically found in heart tissue.

Cardiac infiltration of the extracellular matrix by TTR amyloid fibrils leads to a progressive increase of ventricular wall thickness and a marked increase in chamber stiffness, resulting in impaired diastolic function. Systolic function is also impaired, typically reflected by abnormal longitudinal strain despite a normal ejection fraction, which is preserved until late stages of the disease.[[Castano 2015](#); [Dungu 2012](#); [Mohty 2013](#); [Ruberg 2012](#)] Cardiac infiltration by amyloid can also lead to conduction disturbances and arrhythmias.[[Adams 2016](#); [Ando 2013](#); [Benson and Kincaid 2007](#); [Connors 2004](#)] Patients with symptomatic HF experience rapid progression of their amyloidosis with cardiomyopathy, with substantial worsening of echocardiographic and biomarker measures of cardiac function, in addition to clinical measurements of ambulation, and quality of life. Progression of disease in this population can be seen over a period of 12 months as demonstrated by differences in 6-minute walk test (6-MWT) and Kansas City Cardiomyopathy Questionnaire (KCCQ) – Overall Summary (KCCQ-OS) in the Phase 3 ATTR-ACT study.[[Maurer 2018](#)] Based on natural history data, patients typically experience progressive symptoms of HF resulting in hospitalization and with death typically occurring 2.5 to 5 years after diagnosis.[[Castano 2015](#); [Damy 2015](#); [Dungu 2012](#); [Hawkins 2015](#)]

1.2. Current Treatments

The treatment of ATTR amyloidosis requires a multidisciplinary approach primarily involving cardiology, neurology, and gastroenterology specialties. While there are treatments for polyneuropathy that are available to hATTR amyloidosis patients, for most regions no treatments are currently available for the cardiomyopathy phenotype for either the hATTR or wtATTR forms. Palliative/symptomatic therapies directed at specific symptoms, including volume control and treatment of cardiac arrhythmias and conduction system disturbances, including cardiac pacemakers where appropriate, have been the mainstay of treatment despite their limited effectiveness.

Given that the liver is the primary source of TTR, orthotopic liver transplantation (OLT) has been used for hATTR amyloidosis patients since the early 1990s. However, OLT is intended to eliminate mutant TTR from circulation, but has no effect on the hepatic production of wtTTR, which continues to be made by the transplanted liver and can continue to deposit in the heart. OLT has also only been shown to be effective in slowing the progression of disease in patients with an early age of onset (<50 years of age) [[Okamoto 2009](#)], and especially for those with the V30M mutation and short disease duration before transplant. Consequently, almost two-thirds of patients with hATTR amyloidosis are not transplant-eligible.

Tafamidis, a TTR tetramer stabilizer that acts by binding to the thyroxine-binding site on TTR to reduce its dissociation into misfolded amyloidogenic monomers, is currently approved in a number of markets, but not in the United States (US), for the treatment of patients with hATTR amyloidosis with polyneuropathy.[[Coelho 2016](#)] In addition, tafamidis has been approved in some regions, including the European Union (EU) and US, for the treatment of patients with ATTR amyloidosis (hereditary and wt) with cardiomyopathy based on results from the Phase 3 ATTR-ACT trial.[[Maurer 2018](#)] In Japan, tafamidis was approved for use in transthyretin-type cardiac amyloidosis (wt and mutant), in addition to approval for transthyretin-type familial amyloid polyneuropathy. The ATTR-ACT trial demonstrated that tafamidis treatment over

30 months was associated with lower all-cause mortality and cardiovascular (CV)-related hospitalizations compared with placebo treatment.[\[Maurer 2018\]](#) Additionally, tafamidis treatment resulted in a slowing of the decline in functional capacity (6-MWT) and quality of life (KCCQ-OS) compared to placebo. However, consistent with the expected pharmacodynamic (PD) effect of TTR stabilization, the effects of tafamidis on mortality outcomes was not observed until late in treatment, with differentiation between treatment groups occurring only after 18 months of treatment. Furthermore, although improvements with tafamidis relative to placebo were observed in 6-MWT and KCCQ-OS, minimal changes in echocardiographic parameters were observed, and tafamidis-treated patients still progressed during the study.

The results of the ATTR-ACT study support the general therapeutic hypothesis that modifying TTR has the potential to result in beneficial outcomes in patients with ATTR amyloidosis with cardiomyopathy. However, the disease progression that was observed in both treatment arms in ATTR-ACT highlights an important unmet medical need and suggests that a more direct therapeutic mechanism of action, such as specifically targeting the production of the disease-causing protein with a ribonucleic acid (RNA) interference (RNAi) therapeutic, may be required to halt or reverse the debilitating and ultimately fatal course of disease.

